	• All newborn outcomes will be ascertained until hospital discharge and with 6 week follow-up or death through review of hospital discharge records supplemented by maternal questionnaire at 6 week phone follow-up. Readmissions and related diagnoses for infants will be validated through history and record review.
	• Several data collection forms will be used during these processes, including forms for maternal outcomes, newborn outcomes, NICU outcomes, and postpartum clinic/hospital outcomes. Data on these forms devoid of personal identifiers will be securely sent to the DCC through web-based entry.
	• As a validity check a second abstraction of all study forms will be performed on a random sample of 5% of all subjects by a different research staff and compared for concordance (inter-rater agreement).
	4.5. Follow-up
	• Through discharge and then up to 6 weeks as previously described.
	4.5.1 Withdrawals: Patients who withdraw from the study after randomization will be excluded from further follow-up. Outcomes ascertained up until the time of withdrawal will be reported in intent to treat fashion. Those who withdraw prior to the 6-week window for ascertaining the primary outcome will be accounted for by randomizing an equal number of additional patients.
2.6 Study Duration	3 years
2.7 Statistical Analysis and Sample Size Justification Data Management	Data management: A study statistician and data manager located at UAB will be responsible for coordinating overall data management for the trial. A designated in- country site project director and staff will be responsible for day-today supervision of data management, with everyone using the same standardized data collection tools. Data management at each site includes procedures for data entry, data editing, and compilation; data transmittal and quality control, data verification, confidentiality and security. Data will be collected and managed with Research Electronic Data Capture (REDCap), an established, secure web-based data capture and management tool developed at Vanderbilt University and supported by the Data team at UAB. We have been able to use REDCap for remote capture of data entered in Cameroon into the database at UAB in our ongoing survey of infection practices. Data quality will be assessed monthly by the data manager, and remedial measures, including re-abstraction of data and retraining of staff and edits will be used as needed to enhance data quality.

	Analyses: Data analyses will follow the CONSORT guidelines. Analyses will be by intention-to-treat in which subjects will be analyzed in the group to which they were randomized, regardless of whether or not they received the assigned intervention. Analyses will be performed at the Center for Women's Reproductive Health, University of Alabama at Birmingham. The key analyses for this study are the comparisons reflected by the primary and secondary aims. The primary analysis will compare the incidence of the composite peripartum infection outcome between each of the active groups and the control groups – a chi-square p-value as well as the relative risk and 95% CI will be computed for each comparisons. The secondary outcomes will be similarly compared. Student's t-test comparisons of continuous outcomes will be done. Standard comparisons of covariate characteristics at baseline between groups will be done. It is anticipated that the randomization scheme will balance the groups for these covariates; however, secondary analyses of relevant outcomes using logistic regression adjustments will be implemented to account for any suggested confounding. A secondary comparison will examine the 2 active groups relative to each other. The data from the ureaplasma/mycoplaema_testing_will_be_similarly_compared_with_the
	 Compared with the baseline colonization rate will be reflected by the findings in the no-treatment/placebe group. Sample Size Calculation, Primary Outcome: This has been previously presented above and is shown here as a reminder. Sample size: Up to15-30% of women who have prolonged labor or membrane rupture will have one or more infections included in the primary endpoint. We assume a baseline risk of 20%. To demonstrate a 50% reduction in peripartum infections in the high-risk group of laboring women (of the same order observed in high risk group who have cesarean) with antibiotic prophylaxis with 80% power and alpha of 0.025 per primary comparison (0.05 total), 241 women per group are needed. Thus 750 women will be needed for the 3 arm
	comparison. In a sub-study of our US trial 1/3 (30%) of patients had colonization with ureaplasma or mycoplasma. For the cohort of 600, a sample size of 195 will be needed to estimate a prevalence of 25% (±5%) with 95% confidence. Thus, we will have sufficient study population to estimate the prevalence of colonization with ureaplasmas by PCR methods and to assess its role as a risk factor for infection. Testing of the 200 receiving placebo/placebo will provide baseline prevalence whereas the results from the antibiotic exposed groups will allow us to explore whether the prevalence of ureaplasma/mycoplasma colonization is influenced by the exposure between randomization and delivery (when specimens are collected and stored in
2.8 Specific Drug Supply Requirements	appropriate media). The study drugs and identical placebos will be provided with the assistance of the CBCHS Central pharmacy which is responsible for procuring and supplying medications to over 90 CBCHS facilities in Cameroon. Medications will either be purchased through the CBCHS Central Pharmacy or at a certified pharmacy in the US. The CBCHS pharmacy investigator will be responsible for the destruction of the supplies at the study center pursuant to the ICH/GCP Guidelines, local regulations and the investigator's institutional policies. Clinical supplies will be received by a designated person at the study site, handled and stored safely

11

	and properly, and kept in a secured location for use in study participants. Clinical supplies will be dispensed in accordance with the protocol. The pharmacy is responsible for keeping accurate records of the clinical supplies, the amount dispensed for use by the patients, and the disposition at the end of the study.

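### Section 2.7 tests each primary comparison at alpha 0.025 but plans 95% confidence intervals, so a borderline primary result can fail its test beside an interval that excludes 1

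*Combined protocol and SAP*

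**What the plan says.** Section 2.7 of the combined protocol and SAP deals with the primary comparisons in two places.

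- **Analyses.** "The primary analysis will compare the incidence of the composite peripartum infection outcome between each of the active groups and the control groups". There are two active arms, so there are two primary comparisons. For each, "a chi-square p-value as well as the relative risk and 95% CI will be computed for each comparisons". This text gives no significance threshold.
- **Sample Size Calculation, Primary Outcome.** The trial is sized to detect a halving of a 20% risk at 80% power, with "alpha of 0.025 per primary comparison (0.05 total), 241 women per group are needed". The total is set at 750 for three arms, which is 250 per arm under the 1:1:1 allocation.

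The text available for review does not say whether 0.025 is one- or two-sided, how the interval for the relative risk is computed, whether the chi-square is continuity-corrected, or whether the 95% intervals are adjusted for the two comparisons.

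**The concern.** A 95% interval corresponds to a two-sided test at 0.05, whereas the plan tests each primary comparison at 0.025. When the p-value lies between roughly 0.025 and 0.05, the primary test fails but the interval printed beside it will usually exclude 1. One reader would call that regimen effective from the interval; another would call it unproven from the test.

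Under the present plan the disagreement goes only one way, towards an interval that looks more favourable than the test. If the reporting rule is settled only after the data are seen, the choice could look driven by the result.

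**Working it through.** **1. Sidedness, from the plan's own sample size.** Inputs from section 2.7: p1 = 0.20, p2 = 0.10, power 80%. The pooled two-proportion formula, without continuity correction, is

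n = [z_a √(2 p̄(1−p̄)) + z_b √(p1(1−p1) + p2(1−p2))]² / (p1−p2)²

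with p̄ = 0.15, √(2 × 0.15 × 0.85) = 0.5050, √(0.16 + 0.09) = 0.5 and z_b = 0.8416.

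- Two-sided 0.025: z_a = 2.2414, so n = (2.2414 × 0.5050 + 0.8416 × 0.5)² / 0.01 = 241.1.
- Two-sided 0.05, or equally one-sided 0.025: z_a = 1.9600, so n = 199.0.

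The plan states 241. With continuity correction the figures are 261 (two-sided 0.025) and 219 (one-sided 0.025), and neither matches. The 0.025 is therefore two-sided, and its matching interval has 97.5% coverage.

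**2. How often test and interval disagree.** Assumptions: 250 per arm, a shared control arm, uncorrected Pearson chi-square, and a Wald interval on the log relative risk with SE = √(1/x1 − 1/n + 1/x2 − 1/n), where x1 and x2 are the event counts. All pairs of binomial counts were enumerated exactly. The table gives the probability that p ≥ 0.025 while the 95% interval excludes 1.

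| True risks (placebo / each active arm) | Per comparison | At least one of two |
|---|---|---|
| 20% / 10% (design) | 6.0% | 11.3% |
| 15% / 7.5% | 8.6% | 16.1% |
| 30% / 15% | 1.6% | 3.0% |
| 20% / 20% (no effect) | 2.3% | 4.5% |

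The reverse case, p < 0.025 with a 95% interval that includes 1, has probability 0.0% in all four rows.

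As a cross-check, exact power at 20% vs 10% is 88.7% at 0.05 and 82.3% at 0.025. The difference of 6.4 points is the chance that p falls between the two thresholds, and nearly all of it shows as disagreement.

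Sensitivity: with 241 per arm the design figure is 6.4%; with a continuity-corrected chi-square and 250 per arm it is 9.5%; with a smaller effect (20% vs 13%) and 250 per arm it is 10.6%.

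**3. An example.** Take 50/250 on placebo and 33/250 on active treatment.

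- Relative risk = 33/50 = 0.66; log = −0.4155; SE = √(1/50 − 1/250 + 1/33 − 1/250) = 0.2057.
- Chi-square: pooled risk 83/500 = 0.166, z = 0.068 / √(0.166 × 0.834 × 2/250) = 2.04, p = 0.041. The 0.025 test fails.
- 95% interval: exp(−0.4155 ± 1.9600 × 0.2057) = 0.44 to 0.99, which excludes 1.
- 97.5% interval: exp(−0.4155 ± 2.2414 × 0.2057) = 0.42 to 1.05, which agrees with the test.

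**4. Effect of 97.5% intervals.** A failed test beside an interval that excludes 1 then has probability 0.0% in every scenario run. The reverse case appears instead (p < 0.025 with a 97.5% interval that includes 1): 1.0% of comparisons at 20% vs 10%, 1.4% at 15% vs 7.5% and 0.2% at 30% vs 15%. The width on the log scale grows by 2.2414 / 1.9600 = 1.144, about 14%.

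**The case against.** The strongest reply is that nothing here is a statistical error. The plan asks for a p-value, a relative risk and an interval, and sets the threshold separately. A 95% interval is a valid estimate at its stated coverage whatever alpha the test uses, and with the p-value beside it a careful reader can apply 0.025. All of this stands. What it leaves is that the Analyses text neither repeats the 0.025 nor says the intervals are unadjusted, so the careful reading depends on finding a threshold given only in the sample size text.

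A second reply is that 6% is not a fixed rate. That also stands. It depends on 20% vs 10% and on the assumed test and interval methods, and section 2.2 itself describes the baseline risk as poorly defined. The range should be quoted with it.

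A third reply, that 0.025 is one-sided and so matches a 95% interval, fails: it gives 199 per group, not 241, and the plan presents 0.025 as half of a 0.05 total.

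In the other direction, a reader might infer that the 95% intervals raise the trial's false-positive rate above 0.05. The documents do not support that. The even split across two comparisons is valid, and no text available for review makes the interval the decision rule. By exact enumeration with 20% risk in all arms, the chance of at least one p < 0.025 is 4.6%.

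**Conclusion.** The point holds as a minor inconsistency between interval and test for the primary result. The plan's error control is sound as stated. Under the design assumptions about 6.0% of comparisons, and 11.3% of trials, would show a failed primary test next to a 95% interval that excludes 1. The per-comparison rate is 8.6% to 1.6% over the 15-30% baseline range with halved risk, and 2.3% with no effect.

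These figures rest on 250 per arm, an uncorrected chi-square and a Wald log relative risk interval; the last two are assumptions, since the plan names neither. The mismatch itself depends on neither. That no clarifying label exists can be said only of the text available for review.

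**What to change.** In the Analyses text of section 2.7, state that p < 0.025 (two-sided) decides each primary comparison, and report 97.5% intervals for the two primary relative risks. Sample size, test and endpoint stay as they are.

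The cost is intervals about 14% wider on the log scale and, with Wald intervals, the residual reverse mismatch shown above (1.0% of comparisons at 20% vs 10%, all with a positive test and an interval that includes 1). An interval obtained by inverting the chi-square (score) test should largely avoid that residual, because at a relative risk of 1 its statistic is the uncorrected chi-square; this was not enumerated.

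Optional and separate: applying Holm to the two primary p-values keeps the family-wise error at or below 0.05. At 20% vs 10% it raises power from 82% to 87% per comparison and from 72% to 81% for both. It changes the decision rule and does not by itself align interval and test, so any 95% intervals would need to be labelled as unadjusted and not used for the decision. When only one regimen works (20% on placebo, 20% and 10% on the active arms), the false-positive risk for the inactive regimen rises from 2.5% to 4.2%.

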	membrane rupture). The key primary outcomes will include any maternal bacterial infection (sepsis, chorioamnionitis, endometritis, or other wound infection) and/or maternal death prior to discharge from the hospital. The primary endpoint is the incidence of maternal peripartum infections that lead to sepsis and death. For this study we will assume an effect size of 50% which mirrors the minimum effect size observed with standard antibiotic prophylaxis for cesarean delivery. The baseline risk of infection with prolonged membrane rupture or labor is not well defined and ranges from 15-30%. We assume a baseline risk of 20% for the composite and this test of concept will also help better quantify baseline risks.
2.3 Study Design	Study design:3-arm randomized controlled trial. The investigational regimens are 1g of azithromycin and 1g azithromycin+2g amoxicillin; the common control arm is usual care at sites + placebo. We will design placebo for each, amoxicillin and azithromycin, with the assistance of the CBCHS Central Pharmacy, using identical capsules containing each antibiotic or matching placebo (non-antimicrobial agent e.g. starch) to accomplish blinding: 1 g azithromycin/placebo for amoxicillin, 1 g azithromycin/2 g amoxicillin vs. placebo for azithromycin /placebo for amoxicillin. Study location:4-6 hospitals with approximately 8,000 deliveries in total per year in Cameroon. These hospitals belong to (or are affiliated with) the CBCHS, a well-established major local partner of our UAB Cameroon Health Initiative (CHI UAB). CHI UAB is collaboration between a multidisciplinary group at UAB (multiple schools and departments) and major health organizations in Cameroon including the CBCHS, major medical schools and the Ministry of Health to improve health care through research, education and service delivery. CHI UAB has a dedicated in-country program coordinator based at the CBCHS with a background in laboratory sciences (MSc) and public health (MPH). The CBCHS is a very well organized system with 7 major hospitals and over 80 health care units providing maternity care in 6 of the 10 regions of Cameroon. We will start at BBH, MBH, BHM and Mboppi and add a 5th site later if necessary.

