	Inclusion criteria: Pregnant women with singleton pregnancy in labor at term ≥37 weeks who plan to deliver vaginally and have a) prolonged membrane rupture (≥ 8 hours) or prolonged labor (≥18 hours)* The study is restricted to those at term because those who are preterm may be more likely to receive antibiotics for other reasons and per recommendations. Exclusion criteria: Evidence of chorioamnionitis or other infection requiring antibiotics at time of eligibility, allergy to azithromycin or amoxicillin or any ingredients in the placebo, or plan for cesarean delivery prior to enrollment. Interventions: 1g po Azithromycin/ placebo for amoxicillin, 1g po Azithromycin. Subjects will be stratified by enrollment site.
	develop maternal peripartum infection or death prior to discharge from the hospitalup to 6 weeks postpartum defined as one or more of: a) Chorioamnionitis: Fever (>100.4°F/38°C on two occasions 30 minutes apart or ≥102°F/39°C on one occasion) in addition to one or more of the following: fetal tachycardia >160bpm, maternal tachycardia>100bpm, uterine tenderness or purulent lochia prior to delivery, or diagnosis by a clinician.

1

4

Trained research staff in maternity outcomes reporting at each center (also blinded to study medications) will be responsible for all screening and research data abstraction from patient medical records with the help of clinical investigators and staff. Each hospital will have a designated investigator physician. Research nurses will undergo centralized specific training to screen and ascertain study outcomes. Screening will occur on labor and delivery in the selected CBCHS units and will be conducted by dedicated trained study staff with the assistance of clinical staff. The screening form will be used and completed for each patient screened. Potential subjects will be approached by trained research staff for written consent in English or French. Patients who cannot read will have the consent form read to them. Those that indicate they do not understand will be excluded. Study subjects will be randomized only after eligibility criteria have been confirmed and the patient has consented to participate by signing the informed consent form. The randomization form will be used to complete randomization

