2. Randomization and Drug allocation concealment: Enrolled subjects will be randomly assigned in a 1:1:1 ratio to one of the two prophylactic oral regimens or to no treatment/placebo using either a web-based randomization sequence with varying block sizes and stratified by study site. Alternatively, considering challenges to internet access, a computer-generated randomization scheme with appropriate sequence of use of the interventions will be confidentially maintained in the pharmacy at each site and used to accomplish the random allocation of consecutive patients.

Blinding: As previously discussed we will plan to accomplish blinding with placebo by working with the CBCHS central pharmacy to accomplish identical capsules with and without the active medications. These medications will be packaged according to the predefined sequence into opaque envelopes containing the designated medication. All packages will have capsules that represent azithromycin or placebo and amoxicillin or placebo. The envelopes will be stored in sequential order until a patient is ready for randomization,

3. Medication distribution: The allocated therapy will be provided by the pharmacy staff. Clinical supplies will be received by a designated person at the study site, handled and stored safely and properly, and kept in a secured location for use in study participants as above. Clinical supplies will be dispensed in accordance with the protocol. The pharmacy is responsible for keeping accurate records of the clinical supplies, the amount dispensed for use by the patients, and the disposition at the end of the study.

The allocated therapy will be provided by the pharmacy staff to study staff for distribution.

The patient is considered randomized once the medication is dispensed from the pharmacy and sequential number posted on the patient specific randomization form. The study medication will be initiated immediately (prior to delivery).

On labor anddelivery, achorioamnion swab will be collected by trained research staff into storage tubes with appropriate medium and stored in a dedicated study freezer. Maternal blood will also be collected into the tube provided and frozen as well. Specimens will be shipped to UAB and kept in a biorepository

MISP Protocol and Procedures

I

7

for future testing (shipped in batches as boxes get full). Of note all CBCHS facilities have back-up generators to ensure continuous power.

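### Randomization is stratified by site, but the stated primary chi-square and relative risk leave site out: a small loss, cheaply recovered

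*Combined protocol and SAP*

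**What the plan says.** Site is a design factor. Section 2.3 says "Subjects will be stratified by enrollment site". The procedures on randomization and allocation concealment specify 1:1:1 allocation and leave two routes open. The first is a "web-based randomization sequence with varying block sizes and stratified by study site". The second, for use where internet access is poor, is "a computer-generated randomization scheme with appropriate sequence of use of the interventions" held in each site's pharmacy. Blocking is stated for the first route and not for the second.

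For the number of sites, section 2.3 says "We will start at BBH, MBH, BHM and Mboppi and add a 5th site later if necessary".

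Section 2.7 describes the primary analysis of each active arm against control as "a chi-square p-value as well as the relative risk and 95% CI will be computed for each comparisons". Site does not appear. The only adjustment is a secondary logistic regression, to be used if confounding is suggested, and site is not named there either. A stratified chi-square is not excluded, but none is stated. One part of the protocol, before the newborn-outcome and follow-up text, was not available for this check.

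**The concern.** When allocation is stratified by a factor that predicts outcome, an analysis that ignores the factor does not use the structure of the design. Site could well predict infection here: the control arm is usual care as practised at each hospital, chorioamnionitis can be met by a clinician's diagnosis, and the protocol itself calls baseline risk poorly defined.

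The consequence depends on the allocation route.

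- **Blocked within site.** The arms are balanced at every site, so site differences cancel from the comparison. The crude variance still counts the between-site spread. The standard error is too large, the test slightly conservative and the interval slightly wide.
- **Not blocked.** Arms can be unbalanced by site by chance. The crude variance allows for this, so size and coverage are nominal. The estimate carries avoidable noise, and some power is forgone.

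At stake is a small amount of power and interval width, not the validity of the result.

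**Working it through.** **Inputs from section 2.7.** Control risk 20%, relative risk 0.50 (so 10% on active), alpha 0.025 per comparison, 80% power, 241 per group, 750 in total (250 per arm). Sidedness is not stated; two-sided reproduces the plan's figure.

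**Assumptions.** Four sites of about equal size (62/62/63/63 per arm) and the site-specific risks below, each set averaging 20%. The documents give neither site sizes nor site risks; their 15-30% range is uncertainty about overall risk.

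**1. The plan's sample size.** With pooled variance under the null and mean risk 0.15:

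n = [2.241 × √(2 × 0.15 × 0.85) + 0.842 × √(0.20 × 0.80 + 0.10 × 0.90)]² / 0.10² = 241.1 per group.

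The stated 241 reproduces. Formula power is 80.0% at 241 and 81.6% at 250 per arm.

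**2. Size of the crude test with exact balance within site.** Let r be the average within-site variance divided by the total variance. The actual size at nominal 0.025 is 2 × [1 − Φ(2.241/√r)].

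For site risks 10/15/25/30%:
- within-site: (0.0900 + 0.1275 + 0.1875 + 0.2100)/4 = 0.15375
- total: 0.20 × 0.80 = 0.160
- r = 0.15375/0.160 = 0.961, so size = 0.0222

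The same formula gives 0.0243 for 15/18/22/25% (r = 0.991) and 0.0233 for 15/15/20/30% (r = 0.977).

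**3. Simulation.** 400,000 trials per scenario compare the crude chi-square with the Cochran-Mantel-Haenszel (CMH) test stratified by site. Monte Carlo standard error is 0.00025 for size and 0.06 points for power. Power is at relative risk 0.50.

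| Site control risks (%) | Allocation | Size: chi-square | Size: CMH | Power: chi-square | Power: CMH | CMH gain (points) |
|---|---|---|---|---|---|---|
| 20 at all | blocked | 0.0249 | 0.0249 | 82.3% | 82.1% | −0.2 |
| 15/18/22/25 | blocked | 0.0240 | 0.0247 | 82.5% | 82.6% | under +0.1 |
| 15/15/20/30 | blocked | 0.0228 | 0.0244 | 82.6% | 83.0% | +0.4 |
| 10/15/25/30 | blocked | 0.0218 | 0.0246 | 82.9% | 83.5% | +0.7 |
| 20 at all | unblocked | 0.0254 | 0.0253 | 82.2% | 81.9% | −0.3 |
| 15/18/22/25 | unblocked | 0.0248 | 0.0248 | 82.2% | 82.2% | under 0.1 either way |
| 15/15/20/30 | unblocked | 0.0248 | 0.0247 | 82.2% | 82.6% | +0.4 |
| 10/15/25/30 | unblocked | 0.0246 | 0.0245 | 82.4% | 83.2% | +0.9 |

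Gains are taken from unrounded power. With varying blocks of 3, 6 and 9 (assumed sizes) and an incomplete last block, size at 10/15/25/30% is 0.0223 for the chi-square and 0.0248 for CMH.

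A separate run of 200,000 trials per scenario gave the same pattern and added a wider spread, 5/15/25/35%. There the blocked chi-square has size 0.0193, and CMH gains 1.6 points blocked (84.1% against 82.6%) and 2.0 points unblocked (84.0% against 82.0%).

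**4. Estimate and interval at 10/15/25/30%, relative risk 0.50.**

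| Quantity | Blocked: crude | Blocked: Mantel-Haenszel | Unblocked: crude | Unblocked: Mantel-Haenszel |
|---|---|---|---|---|
| Empirical SD of log relative risk | 0.2308 | 0.2308 | 0.2336 | 0.2316 |
| Coverage of 95% interval | 95.6% | 95.3% | 95.3% | 95.3% |

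Under blocking the two estimates are equally precise, and the crude standard error is on average 1.012 times the stratified one. Without blocking the crude estimate itself is slightly more variable.

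**5. A small late fifth site** (57/57/58/58/20 per arm, fifth site at 20%). CMH size stays at 0.0246 to 0.0249 under either allocation. With equal risks, power for chi-square against CMH is 82.3% and 82.1% blocked, 82.1% and 81.7% unblocked.

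**The case against.** The strongest reply is that the stated analysis is valid and the gain rests on assumed site risks. That is true. The crude test never exceeds its level beyond simulation error, and any departure under blocking is on the safe side. With equal or mildly differing site risks CMH gains nothing or loses a few tenths of a point.

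It is also fair to say that, under blocking, the estimate loses no precision: only its standard error and interval are too wide. A true loss of precision in the estimate arises only without blocking. The two mechanisms should be kept apart, as they are above.

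Third, the secondary logistic regression might take in site. That answers little. It is secondary, depends on confounding being suggested, and does not name site. Under blocking, site would rarely look like a confounder, yet that is where the crude standard error is too large. It would also give an odds ratio rather than the planned relative risk.

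Finally, silence about blocking does not mean that the pharmacy list is unblocked. That stands, and is a reason to have the plan say which it is.

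These replies limit the weight of the point. They do not give a reason to leave a randomization factor out of the primary analysis.

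**Conclusion.** The point holds as a minor one, worth considering. Site is used to randomize and does not appear in the stated primary analysis.

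For site risks within 10-30%, the crude test gives up at most about 0.9 points of power, less than the 1.6 points gained by rounding 241 up to 250 per arm. At 5-35% the loss of 1.6 to 2.0 points equals or slightly exceeds that margin, yet the crude test still has about 82% power. The sample size is not undermined. Conservatism, at worst 0.0218 against 0.025 within 10-30%, appears only when allocation is balanced within site.

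Confidence is high that the available analysis text omits site and that stratifying helps once site risks differ materially. It is low on the size of the gain, which depends on assumed site risks and near-equal site sizes.

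**What to change.** In section 2.7, for each active-versus-control comparison, name as primary the Cochran-Mantel-Haenszel test stratified by enrollment site, with the Mantel-Haenszel relative risk and its confidence interval. Keep the unstratified chi-square and crude relative risk as a sensitivity analysis. Naming the method in advance also settles which chi-square is primary before results are seen.

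In the randomization procedures, state whether the pharmacy-held list is blocked within site, since that decides which of the two mechanisms applies. The stratified analysis keeps its level either way.

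The cost is SAP wording and a few lines of code. Site is known for every woman at enrolment, and no new data or change in sample size is needed. If site risks prove equal, the price is about 0.2 points of power with blocking and 0.3 to 0.4 without.

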Investigator Studies Program (MISP) Protocol and Procedures	
	Section #1 - MISP Protocol Identification
Study Title:	The title of the protocol should include study design, indication and, where applicable, dosage, dosage form, and comparative agent(s). Single oral dose of azithromycin1 gm with or without amoxicillin2 gm to prevent peripartum infection and sepsis in laboring high-risk women: 3-Arm RCT
Request Date:	11/20/2015; Updated 6/13/2017; 10.1.2017; 11.28.17; 10/20/2018
Institution Name	University of Alabama at Birmingham/Cameroon Health Initiative
Investigator Contact Information: – Full address – Phone No. – Fax No. – e-mail address	[name], MD, PhD Professor, Department of Obstetrics and Gynecology Director, Center for Women's Reproductive Health & Maternal-Fetal Medicine Division [name] [contact] [contact] Email: [contact]

Castion #2. Care Brotocal		
	Section #2- Core Protocol	
2.1 Objectives & Hypotheses	Primary Objective : To test the effectiveness of a single adjunctive oral dose of a) 1g of azithromycin and b) 1g of azithromycin + 2g of amoxicillin, each compared to c) usual care alone (placebo group)in reducing maternal peripartum infections and sepsis in at-risk laboring women in a LIC setting. Hypothesis #1 : A single, oral dose of a) 1g azithromycin or b) 1g azithromycin+2g amoxicillin given for prolonged labor or prolonged membrane rupture in term pregnant women will reduce the risk of peripartum infections and sepsis.	
	Secondary Objectives: 1. To collect and story specimens to estimate the prevalence of mycoplasma and ureaplasma in the genital tract, placenta and chorioamnion and assess whether their presence is associated with peripartum infection in LICs.	
	Hypothesis #2: The presence of genitalureaplasma and mycoplasmas in the placenta and chorioamnion of laboring women will be strongly associated with maternal peripartum infections (similar to our findings in the US).	

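### The two primary comparisons appear to rest on a fixed 0.025 split; stating Holm's procedure at familywise 0.05 would add power at the same sample size

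*Combined protocol and SAP*

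**What the plan says.** The primary objective in section 2.1 asks a separate question of each regimen: azithromycin alone and azithromycin plus amoxicillin, "each compared to c) usual care alone (placebo group". Women are "randomly assigned in a 1:1:1 ratio".

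In section 2.7, the sample size paragraph assumes a 20% control rate ("We assume a baseline risk of 20" per cent) and a halving of risk ("To demonstrate a 50% reduction in peripartum infections"). At 80% power and "alpha of 0.025 per primary comparison (0.05 total", it arrives at 241 women per group. The total is then set at 750, which is 250 per arm.

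The Analyses paragraph of section 2.7 compares the composite outcome "between each of the active groups and the control groups", and says that "a chi-square p-value as well as the relative risk and 95% CI will be computed for each comparisons". It repeats no alpha level and names no procedure for handling two primary tests. The comparison of the two active arms is secondary. Section 2.9 states that there is no stopping rule for effectiveness, so no interim spending of alpha has to be considered.

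**The concern.** If the sizing sentence is also the decision rule, each regimen is judged at 0.025 whatever the other comparison shows. A regimen with a p-value between 0.025 and 0.05 would then not be declared effective, even when the other regimen had clearly worked. Its planned 95% interval would usually exclude 1 at the same time, so readers would get two different signals.

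Holm's procedure avoids this loss. It tests the smaller p-value at 0.025 and, if that is significant, the other at 0.05. What is at stake is power to establish each regimen, and both, in a trial that wants an answer on each. A missed effect of azithromycin alone beside a positive combination arm would cloud the choice between a one-drug and a two-drug regimen.

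**Working it through.** **Inputs.** From section 2.7: control 20%, active 10%, 80% power, alpha 0.025 per comparison, 250 per arm (750/3). From the randomization item: 1:1:1. Sidedness is not stated; two-sided is assumed, because the test is a chi-square and because of the next step.

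**Reproducing 241.** Pooled variance, no continuity correction:

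n = [z(1−α/2)·√(2p̄q̄) + z(0.80)·√(p₁q₁ + p₂q₂)]² / (p₁ − p₂)²

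With p̄ = 0.15, z = 2.2414 and 0.8416: n = (2.2414·√0.255 + 0.8416·√0.25)² / 0.01 = 241.1. Power at 241 by this approximation is 79.99%. The alternatives do not fit: one-sided 0.025 gives 199, unpooled variance 238, continuity correction 261.

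**Error control.** If neither regimen works, Holm makes an error only when the smaller p-value is at most 0.025, exactly as Bonferroni does. If one regimen is ineffective, Holm can wrongly reject it only when its own p-value is at most 0.05. The familywise level is therefore 0.05 in every case, and the shared placebo arm is no obstacle.

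**Power.** Let A and B be the two p-values. Bonferroni rejects A if A ≤ 0.025. Holm rejects A if A ≤ 0.025, or if A ≤ 0.05 and B ≤ 0.025. Given the placebo count the two active arms are independent, so the probabilities can be summed exactly over the three binomial distributions. Simulation of 1,000,000 trials per scenario agrees to within about 0.1 point. All tests are two-sided, uncorrected chi-square.

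| Per arm | True rates (placebo, active, active) | Quantity | Split | Holm |
|---|---|---|---|---|
| 250 | 20, 10, 10% | each comparison | 82.3% | 86.6% |
| 250 | 20, 10, 10% | both | 72.1% | 80.7% |
| 250 | 20, 10, 10% | at least one | 92.5% | 92.5% |
| 241 | 20, 10, 10% | each comparison | 80.6% | 85.1% |
| 241 | 20, 10, 10% | both | 69.8% | 78.8% |
| 250 | 15, 7.5, 7.5% | each comparison | 66.8% | 72.2% |
| 250 | 30, 15, 15% | each comparison | 96.6% | 98.0% |
| 250 | 20, 12, 10% | the 12% arm | 58.3% | 66.9% |
| 250 | 20, 20, 10% | the 10% arm | 82.3% | 82.5% |
| 250 | 20, 20, 10% | false positive, 20% arm | 2.5% | 4.3% |
| 250 | 20, 20, 20% | any false positive | 4.6% | 4.6% |

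The 15% and 30% rows are the ends of the protocol's own baseline range. The 12% arm is an illustrative assumption.

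**Cross-check.** Since P(at least one) = P(A) + P(B) − P(both) is the same under both rules, the gain for both must be twice the gain per comparison: 2 × 4.3 = 8.6 points, and 80.7 − 72.1 = 8.6. About one trial in 12 would show one regimen effective under the split and both under Holm.

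**The case against.** The case for leaving the plan alone is respectable.

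- The split is a valid procedure, the sample size is right for it, and the 80% target per comparison is met. The protocol sets no target for showing both regimens effective. All of this stands. A reader might infer that the plan has a multiplicity error or is underpowered because of the split; the documents do not support that.
- The 0.025 appears only in the sizing sentence. A reader might infer that the sponsor has committed to calling a p-value between 0.025 and 0.05 negative, or has weighed and rejected other procedures. The text supplied says neither, and sizing at 0.025 is compatible with a later Holm test. Section 2.7 also refers to an earlier presentation of the sample size that is not in the available text, so a rule stated there cannot be excluded.
- The gain is uneven. It is zero for at least one success, negligible if only one regimen works, and small at a 30% baseline. This stands and limits the size of the point.
- Holm allows more false positives for a single ineffective arm when the other regimen works. This is true, and within the 5% the protocol already accepts in total.
- Intervals that match the fixed split are simple, at 97.5% each. After a second-step Holm rejection, a 97.5% interval can include 1. Preferring the split for that reason is defensible.

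**Conclusion.** The point holds as an optional efficiency gain. Under the protocol's own assumptions, Holm adds about 4 points of power per comparison and about 9 points for both regimens, at 241 or 250 per arm. With a 50% reduction at 250 per arm, the gain per comparison is about 5 points at a 15% baseline and 1.4 points at 30%. In no scenario does Holm have less power than the split.

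This rests on two-sided chi-square tests (sidedness inferred from the 241), on both regimens having some effect, and on the fixed split being the intended rule, which is itself inferred. What the documents show directly is narrower: the Analyses paragraph states no decision rule, and its 95% intervals do not match a 0.025 test. A rule therefore has to be written down in any case, and Holm is the more powerful of the two simple choices.

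**What to change.** In the Analyses paragraph of section 2.7, state before unblinding that the two primary chi-square p-values are tested two-sided by Holm's procedure at familywise 0.05: the smaller against 0.025 and, if significant, the other against 0.05. Keep 241 per group as conservative sizing. Report 97.5% confidence intervals for the two primary relative risks, with a footnote that a second-step rejection can occur when the 97.5% interval includes 1.

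The cost is a sentence on the test, one on the intervals and the footnote, with no additional women. If the sponsor prefers the fixed split for its simpler match with the intervals, that should be stated in the same place.
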